#### 2.3. CLINICAL STUDIES

A first-in-human, double-blind, single ascending dose clinical study (PTI-125-01) was conducted in healthy normal volunteers, age 18-45 with oral dosing solution. Doses were placebo, 50, 100 and 200 mg (equivalent to 31, 62, and 123 mg/m², respectively) administered to three different groups of volunteers. The study showed dose proportional PK, a half-life ranging from 4.5 to 6 h, and there were no drug-related adverse events (AEs).

In a 28-day phase 2a study (PTI-125-03), 13 subjects with mild-to-moderate AD received

simufilam 100 mg b.i.d. as oral tablets. Subjects had Mini-Mental State Exam (MMSE) scores  $\geq 16$  and  $\leq 24$  and were age 50-85 with a CSF total tau/A $\beta_{42}$  ratio  $\geq 0.30$ . A second CSF sample was collected on Day 28, allowing assessment of change from baseline in biomarkers using commercial ELISA kits. All 8 biomarkers that are elevated in AD were significantly reduced from baseline (**Fig. 1**). A $\beta_{42}$ , which is low in AD, was increased slightly but non-significantly. Reduced inflammatory cytokines and YKL-40 indicated reduced neuroinflammation. A reduced neurodegenerative drive was suggested by reductions in neurogranin, neurofilament light chain, and total tau. The robust reduction in phospho-tau (P-tau181) confirms the mechanism of action of simufilam. Simufilam was safe and well tolerated in all subjects.

Figure 1. Phase 2a Mean Change from Baseline to Day 28 in CSF biomarkers (±SEM)

A phase 2b randomized, placebo-controlled clinical study (PTI-125-02) of simufilam 50 or 100 mg tablets or placebo (1:1:1) enrolled 64 mild-to-moderate AD subjects with MMSE 16-26. CSF biomarker analyses were conducted blind to treatment and timepoint by an outside lab, and screening and Day 28 samples for each subject were measured in triplicate in the same ELISA plates. Albumin and immunoglobulin G (IgG) were measured by immunoblotting and quantified by densitometric quantitation. Plasma p-tau181, measured by Quanterix Corporation using their Simoa platform, was significantly reduced versus placebo. The treatment effect on plasma p-tau181 was consistent with treatment effects in CSF biomarkers, suggesting disease modification and replicating Phase 2a results in a well-controlled study. An open-label safety study of simufilam 100 mg showed larger improvements from baseline at 6 months (n=25) (Fig. 2).

[figure not shown]

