#### 3. STUDY OBJECTIVES

The primary objective of this study is to investigate the safety and efficacy of simufilam in slowing cognitive and functional decline following 76-week, repeat-dose oral administration in mild-to-moderate AD subjects, 50-87 years of age. Secondary objectives are to assess neuropsychiatric symptoms and to replicate the CSF biomarker effects observed in the two Phase 2 studies (PTI-125-03 and PTI-125-02) after 76 weeks of simufilam treatment. A third objective is to investigate the effect of simufilam treatment on plasma biomarkers as well as anatomical correlates of disease progression (brain volume [hippocampus, ventricles and whole brain]; amyloid and tau deposition in the brain).

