# 7.2.4. CSF Assays

Approximately 5mL of CSF will be collected and split equally into sterile polypropylene tubes. Following the instructions within the Laboratory Manual, CSF samples are to be frozen (within 30 minutes of collection) and shipped to the central laboratory.

CSF samples will be collected during the Screening Period and again at Week 76 for those subjects participating in the CSF Biomarker sub-study. We currently plan to assay the following biomarkers:

- Total Tau
- P-tau181 and/or P-tau217
- Neurogranin
- sTREM2
- Amyloid-beta 42
- Neurofilament light chain

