# 11.3.3 Other Secondary Analyses

The iADRS is a linear combination of scores from two well-established, widely accepted, therapeutically sensitive measures of AD: the ADAS-Cog and ADCS-iADL (the instrumental component of the ADCS-ADL). The iADRS has been validated and statistical properties of the composite performance have been described. All items of the ADAS-Cog12 and the ADCS-iADL will be included to generate this primary efficacy composite measurement without additional weighting.

Secondary clinical endpoint data (iADRS, NPI, MMSE, and ZBI) measured repeatedly will be analyzed by linear mixed models for repeated measurements, as described above for the primary analysis.

Plasma assays may include P-tau181 and/or P-tau217, SavaDx, neurofilament light chain, and other biomarkers. All plasma biomarker data and MRI data measured repeatedly will be analyzed by linear mixed models for repeated measurements, as described above for the primary analysis.

CSF biomarker endpoints to be analyzed currently include: 1) neurogranin, 2) neurofilament light chain, 3) total tau, 4) P-tau181 and/or P-tau217, 5) sTREM2, and 6) A $\beta_{42}$ . Additional CSF biomarkers may be measured. All CSF biomarker data, PET imaging data, and CDR-SB will be analyzed using ANCOVA models with treatment group as a factor and the baseline value of the corresponding endpoint as a covariate.

All secondary analyses will be conducted using two-sided tests at the alpha = 0.05 level of significance, with no adjustments for multiplicity.

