pre-treatment to post-treatment will be summarized in a shift table. An additional shift table of maximum ideation from pre-treatment to post-treatment will also be provided.

All C-SSRS data will be listed.

All other safety evaluations including urine drug screen results, screening laboratory assessments, Genotyping results collected at Baseline (Study Day 1), and Follow-up Phone Call data will be listed.

10. Changes from Planned Analysis

Not Applicable.

11. Other Planned Analysis

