T14.2.6.4.1	ITT-mild	Summary of Change from Baseline to Week 76 in ZBI Total Score by Visit and Treatment
T14.2.6.6.1	Pooled	Summary of Change from Baseline to Week 52 in ZBI Total Score by Visit and Treatment
T14.2.6.6.2	Pooled	Summary of Change from Baseline to Week 52 in ZBI Total Score by Visit and Treatment Stratified by Baseline Severity Group
T14.2.6.6.3	Pooled	Summary of Change from Baseline to Week 52 in ZBI Total Score by Visit and Treatment Stratified by Baseline Plasma P-Tau Level
T14.2.7.1.1	mITT	Summary of Change from Baseline to Week 76 in CDR-SB Total Score by Visit and Treatment
T14.2.7.2.1	ITT	Summary of Change from Baseline to Week 76 in CDR-SB Total Score by Visit and Treatment
T14.2.7.3.1	cITT	Summary of Change from Baseline to Week 76 in CDR-SB Total Score by Visit and Treatment
T14.2.7.4.1	ITT-mild	Summary of Change from Baseline to Week 76 in CDR-SB Total Score by Visit and Treatment
T14.2.7.6.1	Pooled	Summary of Change from Baseline to Week 52 in CDR-SB Total Score by Visit and Treatment
T14.2.7.6.2	Pooled	Summary of Change from Baseline to Week 52 in CDR-SB Total Score by Visit and Treatment Stratified by Baseline Severity Group
T14.2.7.6.3	Pooled	Summary of Change from Baseline to Week 52 in CDR-SB Total Score by Visit and Treatment Stratified by Baseline Plasma P-Tau Level
T14.2.8.1.1	ITT-plasma	Summary of Change from Baseline to week 76 in Plasma P-Tau 217 by Visit and Treatment
T14.2.8.1.2	ITT-CSF	Summary of Change from Baseline to week 76 in CSF P-Tau 217 by Visit and Treatment
	•	

Version 1.0 | 28-Feb-2025 Page 45 of 56

T14.2.9.1.1	ITT-plasma	Summary of Change from Baseline to week 76 in Plasma Total Tau by Visit and Treatment
T14.2.9.1.2	ITT-CSF	Summary of Change from Baseline to week 76 in CSF Total Tau by Visit and Treatment
T14.2.10.1.1	ITT-plasma	Summary of Change from Baseline to week 76 in Plasma GFAP by Visit and Treatment
T14.2.10.1.2	ITT-CSF	Summary of Change from Baseline to week 76 in CSF GFAP by Visit and Treatment
T14.2.11.1.1	ITT-plasma	Summary of Change from Baseline to week 76 in Plasma NfL by Visit and Treatment
T14.2.11.1.2	ITT-CSF	Summary of Change from Baseline to week 76 in CSF NfL by Visit and Treatment
T14.2.12.1.1	PET	Summary of Change from Baseline to week 76 in tau PET by Visit and Treatment
T14.2.12.1.2	PET	Summary of Change from Baseline to week 76 in amyloid PET by Visit and Treatment
T14.2.13.1.1	MRI	Summary of Change from Baseline to week 76 in Whole Brain Volume by Visit and Treatment

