F14.2.8.1.1	ITT-plasma	Summary of Change from Baseline to week 76 in Plasma P-Tau 217 by Visit and Treatment
F14.2.8.1.2	ITT-CSF	Summary of Change from Baseline to week 76 in CSF P-Tau 217 by Visit and Treatment
F14.2.9.1.1	ITT-plasma	Summary of Change from Baseline to week 76 in Plasma Total Tau by Visit and Treatment
F14.2.9.1.2	ITT-CSF	Summary of Change from Baseline to week 76 in CSF Total Tau by Visit and Treatment
F14.2.10.1.1	ITT-plasma	Summary of Change from Baseline to week 76 in Plasma GFAP by Visit and Treatment
F14.2.10.1.2	ITT-CSF	Summary of Change from Baseline to week 76 in CSF GFAP by Visit and Treatment
F14.2.11.1.1	ITT-plasma	Summary of Change from Baseline to week 76 in Plasma NfL by Visit and Treatment
F14.2.11.1.2	ITT-CSF	Summary of Change from Baseline to week 76 in CSF NfL by Visit and Treatment
F14.2.12.1.1	PET	Summary of Change from Baseline to week 76 in tau PET by Visit and Treatment
F14.2.12.1.2	PET	Summary of Change from Baseline to week 76 in amyloid PET by Visit and Treatment
F14.2.13.1.1	MRI	Summary of Change from Baseline to week 76 in Whole Brain Volume by Visit and Treatment
F14.2.13.1.2	MRI	Summary of Change from Baseline to week 76 in Ventricular Volume by Visit and Treatment
F14.2.14.1.1	MRI	Summary of Change from Baseline to week 76 in Hippocampal Volume by Visit and Treatment
F14.2.14.1.2	MRI	Summary of Change from Baseline to week 76 in Cortical Thickness Volume by Visit and Treatment

Version 1.0 | 28-Feb-2025 Page 56 of 56

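### SAP Tables 6 and 9 plan no CSF output for three of the protocol's six CSF endpoints (neurogranin, sTREM2, Aβ42), and SAP section 10 records no change

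*SAP*

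**What the plan says.** Protocol 11.3.3 gives a numbered list: "CSF biomarker endpoints to be analyzed currently include: 1) neurogranin, 2) neurofilament light chain, 3) total tau, 4) P-tau181 and/or P-tau217, 5) sTREM2", with Aβ42 as the sixth item. Protocol 7.2.4 gives the same six for assay under the words "We currently plan to assay the following biomarkers". Protocol section 3 makes replication of the Phase 2 CSF effects at 76 weeks a secondary objective, and section 4 plans 30 participants per group (90 in all) with lumbar puncture at screening and Week 76. On the Phase 2a result, protocol 2.3 says: "The robust reduction in phospho-tau (P-tau181) confirms the mechanism of action of simufilam".

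SAP Table 6 (section 13.2) has four CSF tables, for P-tau217, total tau, GFAP and NfL. The first is titled "Summary of Change from Baseline to week 76 in CSF P-Tau 217 by Visit and Treatment". Table 9 (section 13.5) has matching figures for the same four, including "Summary of Change from Baseline to week 76 in CSF GFAP by Visit and Treatment". SAP 8.3 describes one ANCOVA for CSF markers in general, with terms for treatment, pooled site and MMSE at baseline, and names no analyte. Table 8 plans one general CSF listing. The SAP section headed "10. Changes from Planned Analysis" is marked not applicable.

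**The concern.** Three endpoints that the protocol says will be analysed disappear from the SAP's list of outputs. Neurogranin, sTREM2 and Aβ42 are named nowhere in the SAP. A reader of the study report would find no summary of them and no explanation, because the section meant for departures declares none.

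What is at stake is a stated secondary objective and the use made of a sub-study that asks participants for two lumbar punctures. If a marker that fell in Phase 2a is never summarised at 76 weeks, replication of that effect is neither shown nor refuted, and the report would not say so.

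The SAP is also unclear about the status of these endpoints. Section 2.1 still calls the fluid markers additional secondary endpoints, and 3.1.2 says early termination changed no secondary objective. Sections 3.1 and 3.1.3 nevertheless place CSF under a third, exploratory objective that does not mention replication.

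**Working it through.** The plan gives no figure to reproduce on this point. The check sets the protocol's list (7.2.4 and 11.3.3) against SAP Tables 6 and 9, and then against the Phase 2a results in the text of protocol 2.3.

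| CSF analyte | Protocol item? | SAP table and figure | Phase 2a, text of protocol 2.3 |
|---|---|---|---|
| Neurogranin | yes | none | reduced |
| NfL | yes | 14.2.11.1.2 | reduced |
| Total tau | yes | 14.2.9.1.2 | reduced |
| P-tau181 and/or P-tau217 | yes | 14.2.8.1.2, P-tau217 only | P-tau181 reduced |
| sTREM2 | yes | none | not named |
| Aβ42 | yes | none | slight rise, not significant |
| GFAP | no | 14.2.10.1.2 | not named |

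**Endpoint list.** Items with an output: NfL, total tau, and the phospho-tau item through its P-tau217 option, so 3. Items without: 6 − 3 = 3, or half the list. Analytes added: 1 (GFAP). SAP CSF outputs: 3 + 1 = 4, which matches Table 6.

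**Replication.** Four Phase 2a reductions named in protocol 2.3 are also on the protocol's list: P-tau181, total tau, neurogranin and NfL. Two of the four (total tau and NfL) keep an output for the same analyte. Neurogranin has none. Phospho-tau is represented by a species other than the one reported in Phase 2a.

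YKL-40 and the inflammatory cytokines, also reduced in Phase 2a, were never among the protocol's six. Their absence is not a SAP change and they are not counted here. On the text of 2.3, sTREM2 and Aβ42 have no significant Phase 2a effect to replicate, so their omission departs from the endpoint list but does not weaken replication. Neurogranin's omission does both.

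**After the fix.** Adding the three missing analytes gives 4 + 3 = 7 CSF tables and covers all six items. Adding P-tau181 would make 8. The same counts apply to the figures.

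**The case against.** The strongest reply is that the protocol's panel is provisional. Both lists are worded as current plans, and 11.3.3 allows further CSF markers, so GFAP is permitted. SAP 8.3 covers any CSF marker measured at baseline and Week 76, a CSF listing is planned, and an overall summary (T14.2.1) takes in exploratory endpoints. On that view only named output shells are missing.

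Part of this stands. The panel may change, and GFAP is not a deviation. But freedom to change the panel does not make a nil entry in section 10 correct. Neither 8.3 nor T14.2.1 names a CSF analyte, and SAP 6.1.8 allows data that are not analysed to appear in listings alone. Nothing therefore commits the analysts to reporting the three markers.

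A reader might infer three stronger things, and the documents support none of them:

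- **That P-tau181 is a fourth dropped endpoint.** The protocol's and/or wording is satisfied by P-tau217. The species matters for replication, not for adherence to the list.
- **That the replication objective cannot be answered at all.** Total tau and NfL, both reduced in Phase 2a, keep tables and figures.
- **That the panel was chosen after seeing results.** SAP 2.1 says learnings from the sister study were used, but the uses spelled out in 2.2 and 6.1.2 concern the analysis population and covariates. Nothing says that study's results informed the CSF panel, and SAP 2.6 says the blind was kept to data lock with potentially unblinding biomarker results withheld or masked.

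The consequence is also limited: this is a small sub-study, its tests have no multiplicity control, and the primary and controlled secondary inferences do not depend on it.

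**Conclusion.** The point holds as a gap between the protocol's endpoint list and the SAP's outputs. Exactly three of six protocol CSF endpoints have no planned table or figure of their own, one marker is added, and section 10 records neither. The replication objective is partly covered: two of the four relevant Phase 2a reductions keep a same-analyte output. It should be corrected, but it does not threaten the main conclusions.

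The conclusion rests on three limits. The Phase 2a count uses the text of protocol 2.3 only, since its figures are not available. The documents do not say whether the omitted analytes were assayed. The 90 participants with paired lumbar punctures are a plan; the study stopped early and the number achieved is not given.

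**What to change.** Add CSF neurogranin, sTREM2 and Aβ42 to SAP Tables 6 and 9, and CSF P-tau181 if it was assayed. Use the CSF ANCOVA with the analyte's own baseline value as covariate, as protocol 11.3.3 specifies; the terms listed in SAP 8.3 leave it out.

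For any analyte not assayed, replace the nil entry in section 10 with its name and a reason dated before unblinding. Where Phase 2a reported an effect on that analyte, state that its replication was not tested. Record GFAP there as an added marker that the protocol permits. Reconcile whether CSF is a secondary or an exploratory objective.

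The cost is some SAP wording and three or four extra tables and figures, together with a few more uncontrolled comparisons in a small sub-study. Sample size, power and alpha are unaffected.

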13.3. Safety Data

Table 7: Safety Data

Table Number	Population	Table Title/Summary
14.3.1 Displays o	f Adverse Events	
14.3.1.1	Safety	Overall Summary of Treatment Emergent Adverse Events
14.3.1.2	Safety	Summary of Treatment Emergent Adverse Events by System Organ Class and Preferred Term
14.3.1.3	Safety	Summary of Treatment Emergent Drug-Related Adverse Events by System Organ Class and Preferred Term
14.3.1.4	Safety	Summary of Treatment Emergent Adverse Events by System Organ Class, Preferred Term, and Maximum Severity
14.3.1.5	Safety	Summary of Serious Treatment Emergent Adverse Events by System Organ Class and Preferred Term
14.3.1.6	Safety	Summary of Treatment Emergent Adverse Events Leading to Study Discontinuation by System Organ Class and Preferred Term
14.3.2 Summary	of Deaths, Other Ser	ious and Significant Adverse Events
14.3.2.1	Safety	Listing of Serious Adverse Events
14.3.2.2	Safety	Listing of Adverse Events Leading to Study Discontinuation
14.3.2.3	Safety	Listing of Adverse Events Leading to Death
14.3.5 Laboratory Data Summary Tables		

Version 1.0 | 28-Feb-2025 Page 46 of 56

[figure not shown]
[figure not shown]

Table Number	Population	Table Title/Summary
14.3.5.1.1	Safety	Summary of Laboratory Results - Serum Chemistry
14.3.5.1.2	Safety	Summary of Shift from Baseline in Serum Chemistry Results
14.3.5.2.1	Safety	Summary of Laboratory Results-Hematology
14.3.5.2.2	Safety	Summary of Shift from Baseline in Hematology Results
14.3.5.3.1	Safety	Summary of Laboratory Results -Urinalysis
14.3.5.3.2	Safety	Summary of Categorical Urinalysis Results
14.3.5.4	Safety	Summary of Stopping Criteria by Treatment
14.3.6 Other Safe	ety Data Summary Ta	ables
14.3.6.1	Safety	Summary of Vital Signs Results
14.3.6.2	Safety	Summary of Weights and BMI
14.3.7.1	Safety	Summary of Concomitant Medications
14.3.7.2	Safety	Summary of Concomitant Medications-Cognitive Enhancers Taken Prior to First Dose of Study Drug
14.3.7.3	Safety	Summary of Concomitant Medications-Cognitive Enhancers Taken Post First Dose of Study Drug
14.3.8.1	Safety	Summary of Electrocardiogram Quantitative Results
14.3.8.2	Safety	Summary of Electrocardiogram Interpretation Results
14.3.8.3	Safety	Summary of Observed Categorical ECGs
14.3.8.4	Safety	Summary of Change from Baseline Categorical ECGs
14.3.9.1	Safety	Summary of Physical Examination (Brief) Results
14.3.9.2	Safety	Summary of Neurological Examination (Brief) Results
14.3.10.1	Safety	Summary of Columbia-Suicide Severity Rating Scale (C-SSRS) Suicidal Ideation and Suicidal Behavior Experienced at Any Time Post-Treatment
14.3.10.2	Safety	Summary of Columbia-Suicide Severity Rating Scale (C-SSRS) Suicidal Ideation and Suicidal Behavior by Study Visit
14.3.10.3	Safety	Shift of Columbia-Suicide Severity Rating Scale (C-SSRS) Suicidal Ideation and Suicidal Behavior from Pre-Treatment to Post-Treatment
14.3.10.4	Safety	Shift of Columbia-Suicide Severity Rating Scale (C-SSRS) Suicidal Ideation Scores from Baseline to Treatment Period
14.3.11.1	MRI Sub-study	Summary of MRI Findings
14.3.5 Other Data Summary Tables		
14.5.1.1	Safety	Summary of Creatinine (umol/L) by Renal Function by Visit
14.5.1.2	Safety	Summary of eGFR (mL/min) by Renal Function by Visit
14.5.1.3	Safety	Summary of Renal Function by Subgroups at Baseline
14.5.2.1	Safety	Summary of TEAEs by Relatedness by Renal Function
14.5.2.2	Safety	Summary of Select TEAEs by Renal Function

Version 1.0 | 28-Feb-2025 Page 47 of 56

13.4. Planned Listing Descriptions

The following are planned data and participant data listings for protocol number PTI-125-06.

In general, one listing will be produced per CRF domain. All listings will be sorted by treatment, and participant number. All calculated variables will be included in the listings.

[figure not shown]
In all listings a blank line will be placed between each participant. Within a data listing, if an item appears line after line (e.g., repetition of participant number), then only the first occurrence will be displayed.

In data listings, the information for one participant will be kept on one page if at all possible, rather than splitting a participant's information across pages.

Table 8: Planned Listings

Data Listing Number	Table Title/Summary
16.2 Subject Data Listing	gs
16.2.1 Subject Discontin	uations/Completions
16.2.1.1	Subject Disposition
16.2.1.2	Inclusion and Exclusion Criteria
16.2.1.3	Subject Randomization
16.2.2 Protocol Deviation	ns
16.2.2	Protocol Deviations
16.2.3 Subjects Excluded	l from the Efficacy Analyses
16.2.3	Analysis Populations
16.2.4 Demographic Dat	a and Other Baseline Characteristics
16.2.4.1	Demographic and Baseline Characteristics
16.2.4.2	Medical or Surgical History
16.2.4.3	Alzheimer's Disease History
16.2.4.4	COVID-19 History
16.2.4.5	Brain MRI
16.2.5 Compliance and/o	or Drug Concentration Data
16.2.5.1	Study Drug Administration
16.2.5.2	Drug Accountability
16.2.5.3	Compliance
16.2.6 Individual Efficac	•
L16.2.xx.xx	Listing of ADAS-Cog Total Score by Treatment, Visit, and MMSE Mild/Moderate Status
L16.2.xx.xx	Listing of ADCS-ADL Total Score by Treatment, Visit, and MMSE Mild/Moderate Status
L16.2.xx.xx	Listing of iADRS Total Score by Treatmen, Visit, and MMSE Mild/Moderate Status

[figure not shown]
Version 1.0 | 28-Feb-2025 Page 48 of 56

Data Listing Number	Table Title/Summary
L16.2.xx.xx	Listing of MMSE Total Score by Treatment, Visit, and MMSE Mild/Moderate Status
L16.2.xx.xx	Listing of NPI-10 Total Score by Treatment, Visit, and MMSE Mild/Moderate Status
L16.2.xx.xx	Listing of NPI-10 Agitation and Aggression Domain Scores by Treatment, Visit, and MMSE Mild/Moderate Status
L16.2.xx.xx	Listing of ZBI Total Score by Treatment, Visit, and MMSE Mild/Moderate Status
L16.2.xx.xx	Listing of CDR-SB Score by Treatment, Visit, and MMSE Mild/Moderate Status
L16.2.xx.xx	Listing of Plasma Biomarkers by Visit and Treatment
L16.2.xx.xx	Listing of CSF Biomarkers by Visit and Treatment
L16.2.xx.xx	Listing of Volumetric MRI Biomarkers by Visit and Treatment
16.2.7 Adverse Event Li	stings
16.2.7.1	Treatment Emergent Adverse Events
16.2.7.2.	Select Treatment Emergent Adverse Events Used for Renal Function
16.2.8 Laboratory Value	es (by Subject)
16.2.8.1.1	Laboratory Results: Serum Chemistry
16.2.8.1.2	Laboratory Results: Hematology
16.2.8.1.3	Laboratory Results: Urinalysis
16.2.8.1.4	Screening Laboratory Assessments
16.2.8.2	Urine Drug Screen
16.2.8.3	Genotyping Sample Collection
16.2.8.4	Pharmacokinetic Results
16.2.8.5	Subjects Who Met Stopping Criteria
16.2.8.6	Creatinine, eGFR, and Renal Function
16.2.9 Other Clinical Ob	oservations and Measurements (by Subject)
16.2.9.1.1.1	Physical Examination (Complete)
16.2.9.1.1.2	Physical Examination (Brief)
16.2.9.1.2.1	Neurologic Examination (Complete)
16.2.9.1.2.2	Neurologic Examination (Brief)
16.2.9.2.1	Vital Signs
16.2.9.3.1	Prior and Concomitant Medications
16.2.9.3.2	Concomitant Medications – Cognitive Enhancers
16.2.9.4.1	12-Lead Electrocardiogram (ECG) Quantitative Results
16.2.9.4.2	12-Lead Electrocardiogram (ECG) Categorical Results
16.2.9.5	Columbia-Suicide Severity Rating Scale (C-SSRS)
16.2.9.6.1	COVID-19 Impact

Version 1.0 | 28-Feb-2025 Page 49 of 56

Data Listing Number	Table Title/Summary	
16.2.9.6.2	COVID-19 Study Drug Impact	
16.2.9.7	Follow-up Phone Calls	

